Roles and responsibilities of different providers	Outline detailed roles and responsibility for each HCW involved in birth dose vaccinations. Develop and train on facility-specific work flows (see section 2.5 above) which will orient HCW to how the birth dose administration fits into maternal and newborn care in terms of sequencing of services, process for recording and reporting and collecting the vaccines (see below), and mitigation plans and reminders (e.g. to follow safe newborn checklist and best practices in terms of handling emergencies first, etc.)		
Policy for birth dose administration	Provide information on updated policy for the birth dose vaccines to be administered in the maternity unit.		
Cold chain storage planning	During the baseline assessment, study members will assess each maternity unit's 24/7 access to a working refrigerator for vaccine storage. Each facility will have a plan (as part of the integrated workflow) on how to access the vaccines immediately after a birth takes place and will be outlined. For facilities without cold chain equipment, a daily schedule (including weekends and holidays) will be implemented where a morning trip is		
	made to the closest health facility or district health service with CCE to pick up vaccines and an evening trip is done to return unused vaccines to the same health facility.		
Recording and reporting harmonization	To ensure birth doses vaccines are properly recorded in both facility records and for the purposes of this pilot study, two record changes will take place and will be described in detail.		
	Birth dose maternity reporting form For the duration of the pilot study maternity units will be provided with a simple recording form with space to document each birth and information on birth doses given. Scenarios for accurately filling out the form will be discussed.		
	Updated birth registry		

	The birth registry will also be updated to include a column to check if the baby received the birth doses of BCG and OPV0 within 24 hours. At the end of each day, this paper will be brought to the EPI unit to incorporate into their record books. In addition, child health cards will need to be stored in maternity units so caregivers can acquire the book at the time of the birth dose administration, and the updated birth dose information is recorded on the health card.

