2.9.3 HCW surveys

To obtain HCW knowledge on birth dose vaccines and corresponding policies, we will conduct HCW surveys (Section 5.4). During the baseline, midline, and end line assessment, HCW's from the 15 facilities will be asked to participate in a survey over the phone with the intention to include a minimum of 3 HCW's from each facility. The survey is expected to take 1 hour and will consist of closed and open-ended questions. The baseline survey will be updated with appropriate language and indicators for the midline and end line survey. Telephone surveys will be scheduled at a time most convenient for the HCW. During the baseline assessment and before any surveys are conducted, copies of the consent form will be left at each facility for survey participants to read through. Prior to beginning the survey, we will read through the consent form to obtain verbal consent. The data collection team will conduct the surveys and will input the participant's survey responses on electronic tablets with all data to be stored on an encrypted server and accessed only by study team members.

Contingency plan:

In the event of worsening COVID-19 transmission and HCW's see a substantial increase in workload with no available time to complete the survey during working hours, surveys outside of working hours will be arranged. If this is required HCW's will be compensated for personal cell phone minutes.

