2.10 Study Outcomes

The primary outcome of this pilot study is change in proportion of newborns receiving birth doses of BCG and OPVO within 24 hours. The key indicators from HCW surveys will be updated to include those from midline and end line surveys and will be sent for review prior to conducting those surveys.

Key Indicator	Source (data	Assessed at	Assessed at	Assessed
	collection tool)	baseline	midline	at end line
Average age of babies at time of	Birth registry and	×		×
receiving birth dose vaccines (BCG	immunization			
and OPV0)	record			
Proportion of babies born/received		×		×
in facilities receiving birth dose				
vaccines (BCG and OPV0) within 24				
hours				
The reason why BCG and OPV0 birth	Birth dose		×	×
dose vaccines were not administered	reporting form			
within 24 hours				
			×	×
			×	×
	HCW survey	×	×	×
Proportion of HCWs that know ideal		×	×	×
timing for birth dose vaccines				

Table 5. List of key indicators and sources

	×	×	×
Reported concerns with administering birth dose vaccines	×	×	×
within 24 hours			
Reported barriers to administering	×	×	×
birth dose vaccines within 24 hours			
Reported barriers to educating	×	×	×
caregivers on birth dose vaccines			
Maternity unit's access to birth dose	×	×	×
vaccines			

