2.12 Data Quality Control Measures and Security

All surveys will be completed in an electronic format using a tablet with incorporated skip patterns to confirm the highest quality data. All data to be stored on a secure server and accessed only by the study team. To minimize data collection errors, daily supervision of data entry into the tablets will be reviewed.

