В2	IN AN IDEAL SITUATION, WHEN SHOULD OPVO VACCINE SHOULD BE ADMINISTERED TO A NEWBORN INFANT, ACCORDING TO EPI NORMS AND STANDARDS? (Read out loud and have the participant select most appropriate)	WITHIN 24 HOURS OF BIRTH	
В3	IN AN IDEAL SITUATION, WHEN SHOULD BCG VACCINE SHOULD BE ADMINISTERED TO A NEWBORN INFANT, ACCORDING TO EPI NORMS AND STANDARDS? (Read out loud and have the participant select most appropriate)	Within 24 hours of birth 1 After 24 h of birth but within two weeks of birth 2 Six weeks of birth 3 After six weeks of birth 4 Don't know 99	

B4	HOW MANY CHILDREN NEED TO BE PRESENT FOR A VIAL OF OPV TO BE OPENED?	[]No. of children Don't Know99	
B5	HOW MANY CHILDREN NEED TO BE PRESENT FOR A VIAL OF BCG TO BE OPENED?	[]No. of children Don't Know99	
B6	IF YOUR FACILITY PROVIDES HEPB VACCINE AT BIRTH, HOW MANY CHILDREN NEED TO BE PRESENT FOR A VIAL OF HEP B TO BE OPENED?	[]No. of children Does not provide HepB birth dose98 Don't Know99	
B7	IS IT RECOMMENDED TO ADMINISTER BCG AT BIRTH TO HEALTHY AND CLINICALLY STABLE LOW BIRTH WEIGHT INFANTS (<2500 GRAMS)?	Yes1 No2 Don't Know99	
B8	IS IT RECOMMENDED TO ADMINISTER OPVO AT BIRTH TO HEALTHY AND CLINICALLY STABLE LOW BIRTH WEIGHT INFANTS (<2500 GRAMS)?	Yes	
	•		
SECTIO	ON 4: General Unit information on	Birth Dose	
SECTIONO.	ON 4: General Unit information on QUESTION	Birth Dose RESPONSE CODE	SKIP
			SKIP
NO.	QUESTION HOW MANY HCWS WORK ON THE	RESPONSE CODE []]	SKIP
NO. CA1	QUESTION HOW MANY HCWS WORK ON THE MATERNITY UNIT? HOW MANY HCWS WORK ON THE	RESPONSE CODE [] No. of HWs Don't Know 99 [] No. of HWs	SKIP

CA5	How does the facility inform MOTHERS ABOUT THE BIRTH DOSE VACCINES? Do not read list. Select all that apply WHAT INFORMATION DO YOU	Pamphlet A Posters	
CA6	PROVIDE TO MOTHERS ABOUT THE BIRTH DOSE VACCINES? Do not read list. Select all that apply	ImportanceB Side effectsC OtherD No information providedX	
CA7	WHAT ARE THE CHALLENGES TO ADMINISTERING A BIRTH DOSE VACCINE WITHIN 24 HOURS OF BIRTH?	[Open-ended]	
CA8	WHERE ARE VACCINES STORED IN THIS FACILITY? Read list. Select all that apply	In Maternity A In EPIB Office of facility in chargeC Other (Please specify)X Don't KnowY	

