CA9	PLEASE SELECT HOW THE VACCINES ARE STORED FOR EACH LOCATION LISTED ABOVE Read list. Select all that apply	A: In Maternity Fridge A Cold Box B Cool Water Pack C Fridge tag D B: In EPI Fridge Fridge tag B Cold Box B Cool Water Pack C Fridge A Cold Box B Cool Water Pack C Fridge tag D C: Office of facility in-charge Fridge A Cold Box B Cool Water Pack C Fridge A Cold Box B Cool Water Pack D	
CA10	Does this facility keep the oxytocin or Vitamin K cold?	A: Oxytocin Yes 1 No 2 Do not have Oxytocin 3 Don't Know 9 B: Vitamin K 9 Yes 1 No 2 Do not have Vitamin K 3 Don't Know 9	A →1 answer CA12, CA13, CA14 B→1 Answer CA14, CA15, CA17 Otherwise, skip to CA18

NO.	QUESTION		RESPONSE CODE	SKIP
SECTIO	ON 5: HCW perspectives			
CA19	WHAT DOES THE MOTHER PAY FOR VACCINATION BOOKLET/CARD?		let []cost Know99	
CA18	IF A VACCINE NEEDED TO BE ACCESSED LATE AT NIGHT OR ON THE WEEKEND, COULD MATERNITY STAFF ACCESS IT?	No		
CA17	Does the maternity unit staff have 24/7 access to vaccines in the immunization unit?	No	1 	
CA16	WHO IS RESPONSIBLE FOR ADMINISTERING VITAMIN K IN THIS FACILITY? Do not read list. Select all that apply	Midw Mater Other	orA rifeB rnity staffC r (Please specify)X KnowY	
CA15	HOW THE IS THE VITAMIN K KEPT COLD? Do not read list. Select all that apply	Cold E Cool V Do no Other	eA BoxB Water PackC ot have Vitamin KD r (Please specify)X r KnowY	
CA14	WHERE IS VITAMIN K STORED IN THIS FACILITY? Do not read list. Select all that apply	In EPI Office Other	aternity A B e of facility in chargeC r (Please specify)X E KnowY	
CA13	WHO IS RESPONSIBLE FOR ADMINISTERING OXYTOCIN IN THIS FACILITY? Do not read list. Select all that apply	Midw Mater Other	orA vifeB rnity staffC r (Please specify)X : KnowY	
CA12	HOW THE OXYTOCIN IS KEPT COLD? Read list. Select all that apply	Cold E Cool V Other	eA BoxB Water PackC r (Please specify)X : KnowY	
CA11	WHERE IS THE OXYTOCIN STORED? Do not read list. Select all that apply	In EPI Office Do no Other	e of facility in charge	

E1	WHAT CONCERNS DO YOU HAVE ABOUT ADMINISTERING OPVO WITHIN 24 HOURS OF BIRTH? Do not read list. Select all that apply	Adverse events following immunization A Inadequate personnel trainingB Inadequate guidance (SOPs)C Uncertainty on contraindicationsD Multiple vaccines administered togetherE No concernsF Other (please specify)X		

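### Two routing rules in the section 5.3 tools lose descriptive Table 5 data: CA10 sends some staff past the 24/7 vaccine-access item, and the newborn form asks no reason for a dose given late

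*Combined protocol and SAP*

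**What the plan says.** **CA10 (section 5.3, HCW Questionnaire).** The item asks separately whether the facility keeps oxytocin cold and whether it keeps vitamin K cold. Each part has four codes: yes, no, product not held, do not know. A yes for oxytocin leads to CA12, CA13 and CA14. For a yes on vitamin K, and for everyone else, the printed rule is "Answer CA14, CA15, CA17 Otherwise, skip to CA18".

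CA17 reads "Does the maternity unit staff have 24/7 access to vaccines in the immunization unit". CA18 asks about late-night and weekend need: "COULD MATERNITY STAFF ACCESS IT". Section 2.12 says the surveys are completed "using a tablet with incorporated skip patterns to confirm the highest quality data". Table 5 (section 2.10) lists "Maternity unit's access to birth dose" vaccines as an indicator from the HCW survey at baseline, midline and end line. Section 2.9.3 plans the survey at each of the 15 facilities "with the intention to include a minimum of 3" workers.

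**Newborn data tool (section 5.3).** For OPV0 and for BCG the form has a yes/no item with no time limit, the date and time of the dose, and a primary reason to be circled only if the answer is no. It is to be completed shortly after discharge. Table 5 lists, from the birth dose reporting form, the reason why the two vaccines were not given within 24 hours.

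**The concern.** The CA10 targets look like numbering left over from another version of the questionnaire. If they are programmed as printed, the tablet will withhold questions from staff who should be asked them. The important one is CA17, which concerns maternity access to vaccines held in the immunization unit. Section 1.3 names poor integration between those two wards as a key concern behind the pilot.

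On the newborn form, the trigger for a reason is that the dose was not given at all, while the indicator is that it was not given within 24 hours. A late dose fails the indicator but passes the trigger.

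Both rules feed Objective 4, on feasibility, barriers and enablers. That objective consists of description, so a lost descriptive item is a real loss, though a small one.

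**Working it through.** The plan states no figure to reproduce. The check sets each routing rule against the item texts and counts the paths.

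**(a) CA10: targets against texts**

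| Item | Subject by its text | On the printed oxytocin route | On the printed vitamin K route |
|---|---|---|---|
| CA11 | oxytocin, where stored | no | no |
| CA12 | oxytocin, how kept cold | yes | no |
| CA13 | oxytocin, who gives it | yes | no |
| CA14 | vitamin K, where stored | yes | yes |
| CA15 | vitamin K, how kept cold | no | yes |
| CA16 | vitamin K, who gives it | no | no |
| CA17 | 24/7 access to vaccines | no | yes |

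CA11 and CA16 are on no route. A vitamin K item is listed under oxytocin, and the vaccine-access item is listed under vitamin K. The rows appear in reverse order in the extracted text, but each number stays with its own question, so the mismatch does not come from extraction.

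Answer pairs: 4 oxytocin codes × 4 vitamin K codes = 16.

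- Vitamin K yes, any oxytocin code: 4 × 1 = 4 pairs. CA17 is listed.
- Neither yes: 3 × 3 = 9 pairs. CA17 is bypassed.
- Oxytocin yes only: 1 × 3 = 3 pairs. No exit after CA14 is stated, so whether CA17 is asked is unsettled.
- Check: 4 + 9 + 3 = 16.

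CA17 is therefore reached in 4 pairs on the literal reading, and in 4 + 3 = 7 if the interview simply runs on after the oxytocin block. The 9 bypassed pairs are the same on both readings. CA18 is reached in 16 of 16. With the targets matched to the texts, CA17 is also reached in 16 of 16.

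Interviews at baseline: 15 facilities × 3 staff = 45 intended.

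**(b) Newborn form: three cases**

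| Dose | Marked | Reason needed by Table 5 | Reason asked |
|---|---|---|---|
| Given at 10 hours | yes | no | no |
| Given at 30 hours, before the form is completed | yes | yes | **no** |
| Not given when the form is completed | no | yes | yes |

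Let T be the hours from birth to completion of the form. The period in which a late dose escapes the reason item is max(0, T − 24) hours. The documents give no length of stay, so T is an assumption: T = 24, 36, 48 or 72 gives 0, 12, 24 or 48 hours. These are widths of a window, not counts of babies.

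**The case against.** The best defence is that little is lost and much of it is covered elsewhere.

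- **Access.** CA18 goes to everyone and covers nights and weekends, which is most of what 24/7 adds. CA8 ("WHERE ARE VACCINES STORED IN THIS FACILITY") and CA9 cover storage. Section 2.7.1 has the study team assess each maternity unit's "24/7 access to a working refrigerator for vaccine storage" at baseline. This stands, and it makes the loss partial.
- **Late doses.** The recorded times of birth and dose still identify every late baby. CA7 asks staff in open form about the challenges of dosing within 24 hours, Table 5 has reported-barrier indicators, and section 2.8 has the forms photographed and reviewed every two weeks, with a call. This stands too, but none of it supplies a coded reason for each baby.
- **Piloting.** Section 2.7.2 tests the tools in 2 facilities and allows edits. That may catch both errors, although nothing directs it to the routing.

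Four stronger readings are tempting and are not supported.

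- A reader might multiply 45 by three rounds and say that 135 interviews are affected. Section 2.9.3 says the baseline survey will be updated for midline and end line, and section 2.10 sends the updated survey indicators for review first. Only the baseline form is before us, and three staff per facility is an intention.
- A reader might see a conflict between section 2.9.2, which has the form filled out after each birth, and the tool's own instruction to complete it shortly after discharge. The second is only more specific; the two are compatible.
- A reader might suspect the B1 skip rule as well. B1's answer list is cut in the extracted text, so its codes cannot be read and no error can be shown.
- A reader might infer that missing CA17 answers cluster where vaccine cold chain is weakest. CA10 concerns oxytocin and vitamin K, and section 2.5 already requires cold chain equipment on site or within one km.

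**Conclusion.** Both routing rules are wrong as written for the indicators they serve, and the point is minor. The primary outcome comes from the registers and is unaffected.

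For (a), CA11 and CA16 are never asked, and CA17 is certainly bypassed in 9 of 16 answer pairs. The documents give no distribution of answers, so this cannot be turned into a share of staff. The exposure is about 45 intended baseline interviews, and later rounds only if the planned update leaves the rule as it is. This assumes that the tablet follows the printed rule.

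For (b), the coded reason is missing for doses given after 24 hours but before the form is completed. How many babies that involves is unknown and may be few. This part assumes that the newborn data tool is the birth dose reporting form of section 2.9.2; it is the only per-birth form in section 5.3.

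**What to change.** **CA10.** Send oxytocin yes to CA11–CA13 and vitamin K yes to CA14–CA16; otherwise skip to CA17. Ask CA17 and CA18 of every respondent. Make the same change on the printed form and in the tablet logic.

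**Newborn form.** For OPV0 and for BCG, change the trigger to: *If No, or if given more than 24 hours after birth, circle the primary reason.*

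**Test.** In the two-facility pilot of the tools, run one interview path with neither product kept cold and one form with a dose given after 24 hours. Confirm that CA17 and the reason item appear.

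**Cost.** A renumbering and one line per vaccine, made before baseline. Section 2.7.2 already provides for edits to the tools after piloting.

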2.8 Ongoing trouble-shooting touch points

To enable touch points to discuss problems during the 12-week intervention and foster a relationship between the study team and maternity staff, ongoing monitoring of the intervention will occur. Due to

COVID-19, this will be occurring remotely. Every two weeks the head of the delivery unit will take a photo of the birth dose maternity reporting forms and send it to the study team for review of progress. Once the photo is obtained a brief telephone conversation will occur to troubleshoot immediate challenges, check on the pilot study progress, and to further strengthen the relationship.

Contingency plan:

In the event of worsening COVID-19 pandemic and facilities see a large increase in case load, scheduling the phone meetings will be delayed until it is reasonable to continue.

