2.9.2 Birth dose reporting form

To obtain information on the specifics of the birth dose administration, the reporting forms created for this pilot study will be used (Section 5.4). After each birth, a member of the maternity unit staff will fill out the birth dose reporting form, in addition to normal recording procedures. As part of the ongoing supervisory check-in the reporting forms will be sent through email or WhatsApp to study members for brief review. While data collectors are at each facility for registry extraction at end line, they will collect the completed birth dose reporting forms.

Contingency plan:

As the hard copy forms will be gathered at the end line of the study, in the event of worsening COVID-19 transmission, data collectors will delay collecting the birth dose reporting forms until it is safe to do so.

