For sampling interval, count how many children are entered within a year of today's date. Divide this total number by 30 to get your sampling interval. For instance, if there are 300 children within the year, your sampling interval is 300/30 or 10. Therefore, you will enter every 10th child until you reach 30 children in total. For this work you will also be looking the child up in the immunization register. Please ask the in-charge and the EPI nurse to gather this information when it is not in use.

	Delivery register			Immunization register									
Child Name	Q1. Date of Birth	Q2. Date of OPV0 administered	Q3. Date BCG administered	Q4. Were you able to find this child based on name	Q5. Date of OPV0 administered	Q6. Date BCG administered							
	A - Date of birth listed? 1 = Yes, 2 = No (If no, skip Q1.B)	A – Was vaccine administered? 1 = Yes, 2 = No (If no, skip Q2.B)	A – Was vaccine administered? 1 = Yes, 2 = No (If no, skip Q3.B)	and birth date in the register? 1 = Yes, 2 – No (if no, skip Q5 and Q6)	A – Was vaccine administered? 1 = Yes, 2 = No (If no, skip Q5.B)	A – Was vaccine administered? 1 = Yes, 2 = No (If no, skip Q6.B)							
	B - Date listed C – Time of Birth	B - Date listed C – Time of vaccine administration	B - Date listed C – Time of vaccine administration		B - Date listed C – Time of vaccine administration	B - Date listed C – Time of vaccine administration							

Newborn data tool

This form should be used to record data about each delivery during the study period. Data should be completed by a delivery nurse and shortly after the baby is discharged.

Child #:	Facility		Date:	//
	Code:			

Delivery Inform	nation	OPV0→	
Gender	Male1 Female2	OPV0	Yes1 No2
Date of birth, Time of birth, and birth weight	/ : : (DD/MM HH:mm) Grams	DATE AND TIME THE BABY RECEIVED OPVO	/ : : (DD/MM hh:mm)
CIRCLE ALL SERVICES PROVIDED	EPI visitA Dr visitB PNCC OtherX If other, specify:	IF NO, PLEASE CIRCLE THE PRIMARY REASON	Caregiver refused1Stock out2Scheduled for later3EPI was not open4Left before receiving the vaccine6Too few children to open a vial7Not eligible for clinical reasons8Not enough time for vaccination9Other10If other, specify:
OXYTOCIN GIVEN?	Yes1 No2	BCG→	
DISCHARGE DATE AND TIME	/ :	BCG	Yes1 No2
PLEASE LIST ANY CC	MPLICATIONS OR COMMENTS ON THE BIRTH:	DATE AND TIME THE BABY RECEIVED BCG	/ ::
		IF NO, PLEASE CIRCLE THE PRIMARY REASON	Caregiver refused

Notes for touchpoint calls

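### The birth dose form asks for a reason only when a vaccine was not given, so late doses given before discharge drop out of the indicator on why doses were not given within 24 hours

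*Combined protocol and SAP*

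**What the plan says.** In Table 5 of section 2.10 the indicator begins "The reason why BCG and OPV0 birth" and continues over the broken lines of the table to doses not administered within 24 hours. Its source is the birth dose reporting form, and it is assessed at midline and end line.

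No tool in section 5.3 carries that name. The Newborn data tool is the only one completed for each delivery with the birth doses recorded, so I take it to be the form meant. For OPV0 and for BCG it has a Yes/No item, a field for when the dose was given (for BCG, "DATE AND TIME THE BABY RECEIVED BCG"), and a list of reasons under "IF NO, PLEASE CIRCLE THE PRIMARY REASON". It also has a field "DISCHARGE DATE AND TIME". Its instruction reads "Data should be completed by a delivery nurse and shortly after the baby is discharged".

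Section 2.11 plans means and proportions from these forms and gives no rule for deriving the reason indicator.

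**The concern.** The indicator concerns doses not given in time. The form asks about doses not given at all by the time it is filled in. The two differ for babies who stay beyond 24 hours and are vaccinated late during that stay.

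These babies are of direct interest. Section 1.3 says that most facilities vaccinate only on designated days. Several of the form's reason codes (immunization unit not open, scheduled for later, too few children to open a vial) could equally explain a late dose during the stay. The form shows that such a dose was late but not why, and a reason not asked for at the time may not be recoverable afterwards.

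**Working it through.** No sample size, power or error rate bears on this point, and the plan gives no figure to reproduce. The check compares what the form asks with what the indicator needs.

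Let t be the age at dose (infinite if never given) and d the age at discharge, taken as the time to which the completed form refers. The form asks for a reason when t > d. Table 5 needs one when t > 24 h.

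- t ≤ 24 h and t ≤ d: marked Yes, no reason asked, none needed. Match.
- t > 24 h and t ≤ d: marked Yes, no reason asked, but one is needed. **The late dose is omitted.**
- t > 24 h or never given, and t > d: marked No, reason asked and needed. Match.
- t ≤ 24 h and t > d: marked No, reason recorded, none needed. This case is conditional and is taken up under the objection.

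The second case follows directly from the printed form. Its frequency cannot be computed, because the documents give neither length of stay nor the distribution of dose times.

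The effect on a reported percentage can be shown only on assumed values. Let p be the share of a given reason among babies marked No (all taken here as untimely), f the share of all untimely babies who were vaccinated late before discharge, and q the unknown share of that reason in the omitted group. Then

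true share = (1 − f)p + f·q, with q between 0 and 1.

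For an assumed p = 30%:

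- f = 0: 30%, no distortion.
- f = 5%: 0.95 × 0.30 = 28.5% up to 28.5% + 5% = 33.5%.
- f = 10%: 0.90 × 0.30 = 27% up to 27% + 10% = 37%.

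These are worst-case limits, and in general the direction is unknown. One code is an exception: a baby vaccinated before discharge cannot have left before receiving the vaccine, so q = 0 for that code. Omitting late doses can then only overstate its share, and the true value is (1 − f) times the form value.

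**The case against.** The strongest reply is that other parts of the plan fill the gap. Training covers the form ("Scenarios for accurately filling out the form will be discussed"). The forms are reviewed every two weeks, and "Once the photo is obtained a brief telephone conversation will occur to troubleshoot immediate challenges". The touchpoint notes record stock-outs and cold chain problems, the form has space for comments, and the HCW survey collects reported barriers at three time points. Objective 4 therefore does not rest on this item alone. That stands, and it limits the harm. But none of these is specified to obtain a reason for each late baby, or to tell staff to read No as not within 24 hours.

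Three stronger readings are tempting, and the documents do not support them.

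- A reader might infer that the form also miscounts timely doses as untimely. That needs discharge before 24 hours without the dose, then a dose still within 24 hours, after the form has been closed. This is possible, but nothing in the documents shows that it occurs. The designated vaccination days in section 1.3 and the move of vaccination into the maternity unit make it less likely.
- A reader might see a conflict with section 2.9.2, which says "After each birth, a member of the maternity unit staff will fill out the birth dose reporting form". This reads naturally as meaning for every birth, and the discharge field means that the form cannot be finished before discharge.
- A reader might combine both errors to obtain a wide range for the reported percentages. Every input to such a range would be assumed.

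Two reading limits remain. The identity of the form is an inference, and some rows of Table 5 have no readable text, so other indicators based on the form may not be visible.

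**Conclusion.** The point holds for late doses given before discharge. Followed as printed, the form collects reasons from a group that is not the one Table 5 names, and section 2.11 has no rule that corrects for this. The conclusion rests on the Newborn data tool being the birth dose reporting form and on staff marking Yes for any dose given by the time of completion.

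The size is unknown and may be small; the ranges above illustrate and do not estimate. A reader might infer that the 24-hour coverage result is compromised. It is not, because that outcome comes from the birth and immunization registers. What is affected is one descriptive barrier indicator for objective 4. The change is still worth making because it costs almost nothing and is best done before the forms are printed.

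**What to change.** 1. On the form, for both OPV0 and BCG, change the condition to: *If not given within 24 hours of birth (not given, or given later), circle the primary reason.*
2. Explain this in the form-filling scenarios already planned for training (section 2.7.1, Table 4).
3. In the two-weekly form review (section 2.8), ask for the reason for any late dose where none is recorded.
4. In section 2.11, use the form's birth, dose and discharge times to tabulate reasons separately for doses given late before discharge, doses not given by a discharge at or after 24 hours, and doses not given by a discharge before 24 hours. Report the last group apart, as not given by discharge with 24-hour status not known.

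The new wording alone does not settle that last group, which is why it is kept separate. No register look-up is required. The form shows a child number but no name, whereas section 2.9.1 matches records by name and date of birth and describes the immunization registry as holding dates.

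The cost is one line per vaccine on the form, a few lines in section 2.11, a few seconds more per late baby and a small extra table. No additional visits or training sessions are needed.
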